Study size	
To reach a precision of < 20% for the primary outcome pain response, 300 patients have to be included, based on the following assumptions: 70% of patients will be evaluable for the primary analysis of pain response at a post-baseline assessment and 30% to 70% of patients show a pain response.
 
300 patients is a realistic estimate to be enrolled in a two-year enrollment period, based on current patient numbers and available sites for the treatment. With this sample size and a pain response rate of 65% a precision of < 20 % can be reached assuming subgroups to be at least of 1/2 of this size.

Data analysis	
Statistical analyses will be primarily of explorative and descriptive nature. Whenever reasonable, data will be stratified by subgroups (i.e. age, other baseline characteristics).
 
Patients receiving at least one dose of Radium-223 will be considered valid for safety analysis set.
 
Analyses of pain or QoL will be performed for patients with evaluable patient questionnaires (BPI-SF, FACT-BP, respectively) at baseline and at least one post baseline visit. The incidence proportion will be provided, along with the exact 95% confidence interval. A clinically increase or decrease in opioid use will be taken into account as will be defined in the SAP.
 
The primary analysis of pain response will be summarized in the population of patients with a score >1 (0="no pain") for the baseline measurement of the 'Worst Pain'-item of the BPI-SF.
 
Pain, including subgroups considered as covariates, and quality of life assessments will be summarized descriptively including mean and change from baseline. An analysis of covariance model will be used to assess changes in pain severity.
 
Time to event variables (TTNT, SSE, OS) will be summarized using Kaplan-Meier estimates. Median event times together with the 25th and 75th percentiles and associated 95% confidence intervals will be presented.
 
All therapies documented will be coded using the World Health

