8.2 Secondary objective(s)

The secondary objectives in this study are:

- To evaluate the change of pain and bone pain related quality of life over time during treatment phase.

- To evaluate pain control rate.
- To evaluate pain progression rate
- To evaluate time to first pain progression.
- To evaluate time to first opioid use.
- To evaluate covariates on pain response of mCRPC patients during treatment phase.
- To evaluate pain response related to the extent of bone metastases at baseline
- To evaluate the relation between bone uptake in known lesions and pain palliation (only in patients with bone scan prior to start of treatment and a second scan during or within 6 weeks after end of Radium-223 treatment).
- To evaluate Radium-223 treatment patterns
- To evaluate the course of blood counts in patients with different extent of disease and in the whole patient population.
- To determine treatments and time to subsequent mCRPC treatment (TTNT).
- To determine the time to first symptomatic skeletal event (SSE).
- To determine overall survival (OS).
- Treatment-emergent adverse events (TEAE) (up to 30 days after last administration of Radium-223).

9 Research methods

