9.1 Study design

This study is a prospective, non-interventional, multi-center, single arm cohort study conducted in nuclear medicine clinics and practices throughout Germany. Sites are selected based on the experience of the attending physician with the indication and the treatment with Radium-223. It is planned to enroll 300 patients with CRPC with bone metastases for whom the attending physician decided according to his/her medical practice to treat the patient with Radium-223. Treatment with Radium-223 should follow the approved product information.

For each patient, the investigator will document data in standardized case report forms at initial, follow-up and final visits during treatment phase. Data will be collected using electronic case report forms (eCRF). The observation period for each patient enrolled in this study is the time from start of therapy with Radium-223 to death, withdrawal of consent, loss to follow-up or end of this study (maximum of 2 years after last administration of Radium-223), whichever comes first in time.

The medication is used within the routine clinical practice setting. Commercially available product will be used to treat the patients.

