9.7.5 Analysis of secondary outcome(s)

- Change of pain over time: The responses to each of the BPI-SF items and the following two dimensions which are aggregated from BPI-SF items will be summarized descriptively:
 - Pain severity index:

It uses the sum of the four items on the pain intensity. All four severity items must be completed for aggregating the pain severity index.
 - Pain interference index:

It uses the sum of the seven pain interference items. The pain interference index is scored as the mean of the item scores multiplied by seven, given that at least four of the seven items have been completed.

Summary statistics, including mean and change from baseline, will be provided for each assessment time point. For the summary of each post-baseline assessment, patients will be excluded if there is no corresponding post-baseline measurement.

- For bone pain related quality of life assessment summary statistics including mean and change from baseline will be provided for each assessment time point of the FACT-BP questionnaire. For the summary of each post-baseline assessment, patients will be excluded if there is no corresponding post-baseline measurement.
- Pain control rate will be summarized. Pain control is defined as no increase by two or more points from the baseline measurement of the ‘Worst Pain’-item of the BPI-SF (Question 3) at any post-baseline assessment.
- Pain progression rate will be summarized. Pain progression is defined as two or more points increase from the baseline measurement of the ‘Worst Pain’-item of the BPI-SF (Question 3) at any post-baseline assessment.
- Time to first pain progression will be summarized by Kaplan-Meier (KM) estimates.
- Pain response will be additionally summarized descriptively for the subgroups defined in ‘evaluation of covariates on pain response’ in Section 9.1.2.

An analysis of covariance model will be used to assess changes in pain severity, as measured by the worst pain score on the BPI-SF, at each post-baseline assessment time point. The baseline worst pain score will be used as a covariate in each analysis of covariance model.

- The relation between bone uptake in known lesions and pain palliation will be analyzed (only in patients with bone scan prior to start of treatment and at least one further documented bone scan during or after end of Radium-223 treatment).

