- The course of blood counts will be analyzed. Incidence of blood counts below limit for further injections according to the local product information in patients with different extent of disease

and in the whole patient population will be calculated. The incidence proportion will be provided, along with the exact 95% confidence interval.

- Time to event variables (TTNT, SSE, OS) will be summarized using Kaplan-Meier estimates. Median event times together with the 25th and 75th percentiles and associated 95% confidence intervals will be presented. Censoring rules will be defined in the SAP.
- Incidence of treatment emergent and drug-related AEs will be presented using the NCI-CTCAE Version 4.03. Additional subcategories will be based on event intensity and relationship to study drug.

Further details will be given in the SAP.

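### The single-arm ANCOVA of worst pain names baseline as its only term, so it returns the raw mean change, and any model-based interval would be too narrow for the population mean

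*Protocol*

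**What the plan says.** Section 9.1 describes the design: "This study is a prospective, non-interventional, multi-center, single arm cohort study conducted in nuclear medicine clinics and practices throughout Germany". There is no comparator group.

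For change in pain, Section 9.7.5 plans summary statistics (mean and change from baseline) at every assessment. It then adds a model: "An analysis of covariance model will be used to assess changes in pain severity, as measured by the worst pain score on the BPI-SF", fitted for each post-baseline visit. One model term is named: "The baseline worst pain score will be used as a covariate in each analysis of covariance model". No factor, other covariate or target quantity (adjusted mean, slope or test) is given. The data analysis entry of the abstract (Section 4) mentions the ANCOVA in one sentence and also names no factor.

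The covariates are dealt with elsewhere. The objective in Section 8.2 is "To evaluate covariates on pain response of mCRPC patients during treatment phase", and the matching analysis in Section 9.7.5 is "Pain response will be additionally summarized descriptively for the subgroups defined in ‘evaluation of covariates on pain response’ in Section 9.1.2". Section 9.7.5 closes with "Further details will be given in the SAP".

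**The concern.** ANCOVA compares groups after adjusting for a covariate. Here there is one group, and only the adjusting covariate is named. A model with an intercept and baseline worst pain has nothing to adjust, because its mean at the average baseline is the observed mean change.

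What does change is the standard error. Default output bases it on the residual variance and leaves out the sampling variation of baseline itself. A reader who sees an adjusted mean change with its confidence interval will take it as more precise than the raw mean change, although the point estimate is identical. Section 9.9 expects results to be set beside historical data, and there an interval that is too narrow overstates certainty.

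The other output, the slope on baseline, is hard to interpret. With equal SDs it equals the correlation minus 1 (for example -0.5 at a correlation of 0.5) even when mean pain does not change at all, which is regression to the mean.

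**Working it through.** **Inputs from the protocol.** One arm (9.1); one model per post-baseline visit with baseline worst pain as the named term (9.7.5); 300 patients, 70% evaluable, so 300 × 0.70 = 210 (9.5). The protocol gives no figure for the ANCOVA. The nearest figure of its own, Table 3, reproduces: at a response rate of 0.65, 0.65 ± 1.96 × √(0.65 × 0.35 / 210) gives 0.585 to 0.715, as printed. Table 3 does not depend on the ANCOVA.

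**Assumed inputs, not in the protocol.** Equal SD s at baseline and follow-up; correlation r between them of 0.3, 0.5 or 0.7, with 0.9 as a favourable case.

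**Step 1: point estimate.** A least-squares line with an intercept passes through the point of means. At the sample mean baseline the fitted change is therefore the mean change. In simulation the two differed by at most about 1e-15.

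**Step 2: standard errors.**
- Paired: Var(change) = 2s²(1 − r), so SE = √[2s²(1 − r)/n].
- ANCOVA at the mean baseline: residual variance = s²(1 − r²), so SE = √[s²(1 − r²)/n].
- The missing piece is slope² × Var(baseline) = (1 − r)²s². Adding it back gives s²(1 − r²) + s²(1 − r)² = 2s²(1 − r), the paired variance.
- Ratio, ANCOVA to paired: √[(1 − r²)/(2(1 − r))] = √[(1 + r)/2]. It does not depend on n.

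**Step 3: coverage of the population mean change** by a nominal 95% interval is 2Φ(1.96 × ratio) − 1.

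| r | SE ratio | Coverage |
|---|---|---|
| 0.3 | √0.65 = 0.806 | 88.6% |
| 0.5 | √0.75 = 0.866 | 91.0% |
| 0.7 | √0.85 = 0.922 | 92.9% |
| 0.9 | √0.95 = 0.975 | 94.4% |

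**Step 4: simulation** (n = 210, 4,000 runs per r, normal scores, SD 2 at both times, random baseline). For r = 0.3, 0.5 and 0.7 the mean SE ratio was 0.806, 0.865 and 0.921. The ANCOVA interval covered 89.0%, 91.4% and 92.9%; the paired t interval covered 95.1%, 95.4% and 95.0%.

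**Step 5: unequal SDs.** With k = follow-up SD / baseline SD, the ratio is √(1 − R²), where R² = (rk − 1)²/(1 + k² − 2rk). For k from 0.8 to 1.2 and r from 0.3 to 0.7 it runs from 0.709 (k = 0.8, r = 0.3) to 0.983 (k = 1.2, r = 0.7).

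**Step 6: is baseline-only the right reading?** The text never says so. Three things favour it. The reference to each model follows directly on the reference to each visit, so one model per visit is the natural sense. The subgroup bullet above it concerns a different, binary endpoint and is descriptive, and the abstract agrees: "Pain, including subgroups considered as covariates, and quality of life assessments will be summarized descriptively including mean and change from baseline". The ENCePP checklist in Annex 2 answers No on methods for adjusting for confounding (10.5) and for effect modification (10.6), which would be odd if the Section 9.1.2 covariates were factors in this model.

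**The case against.** The strongest reply is that the protocol does not state the model criticised here. Naming baseline as a covariate does not make it the sole term, an ANCOVA ordinarily carries a factor, the paragraph stands just below the subgroup bullet, and the details are left to an SAP that is not shown. This stands to the extent that baseline-only is an inference. It is the best-supported reading but not a certain one.

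Two further points also stand. The ANCOVA standard error is correct for the mean change conditional on the observed baselines. It falls short only for the population mean, which is nevertheless what a study seeking representative patients (9.1.3) and consecutive enrolment (9.2.6) wants to describe. And the raw mean change is already planned, so a sound estimate will be available in any case.

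Two stronger readings are tempting, and the protocol supports neither:
- A reader might infer that the planned confidence intervals for change in worst pain are wrong. The protocol promises no ANCOVA-based interval. It states its intervals for pain response, blood counts and the Kaplan-Meier quantiles, and none for this model. The undercoverage arises only if model-based intervals are reported.
- A reader might infer that the covariate objective goes unanswered. That objective concerns pain response and has its own descriptive subgroup summaries. The ANCOVA addresses a different outcome and leaves no gap there.

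**Conclusion.** The point holds in a limited form. The protocol chooses a model for comparing groups in a study with one group and names only the adjustment term. Read that way, the model adds nothing to the planned mean change except a standard error that is too small for the population mean: by about 8% to 19% for correlations of 0.7 down to 0.3 with equal SDs, and by about 2.5% at 0.9. The shortfall could reach 29% if follow-up scores vary less than baseline scores (SD ratio 0.8, correlation 0.3). All these sizes rest on assumed correlations and SDs, and on the population mean change being the target.

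If a subgroup factor was intended, the model is sensible but the factor must be named. The sentence needs correcting on either reading. Severity is low: the analysis is secondary and exploratory, and neither the primary endpoint nor the sample size depends on it.

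**What to change.** For the overall change in worst pain at each visit, report the mean paired change with its t-based 95% CI. Keep the ANCOVA only where it estimates a contrast: one named baseline factor from Section 9.1.2 per model (for example extent of bone metastases, or prior chemotherapy) with baseline worst pain as covariate, reporting adjusted differences between categories with 95% CIs, labelled exploratory.

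The cost is a few sentences in the SAP, a few lines of code and a little more analysis work. Intervals for the overall change will be wider than the model-based ones, by 1/0.922 = 1.08 to 1/0.806 = 1.24 times under the assumed correlations of 0.7 to 0.3. That is the width needed for about 95% coverage.

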The development of bone metastases is a serious threat to the patients’ quality of life and survival, with survival being impacted by the number of metastases. Approximately 50% of patients with bone-metastatic prostate cancer die of prostate cancer within 30 months, and 80% within 5 years [11]. The associated complications present a substantial disease and economic burden [12]. Untreated patients face severe morbidity, including bone pain, bone fractures, compression of the spinal cord and hematological consequences of bone marrow involvement such as anemia. As presence of bone metastases represents a major clinical problem for patients with metastatic castration-resistant prostate cancer (mCRPC), specific treatment options for this condition are needed. Control of bone metastases is expected to lead to improved symptoms and quality of life as well as prolonged overall survival.

Radium-223 selectively targets bone metastases with high-energy, short-range alpha-particles. A phase III, double-blind, randomized trial, ALSYMPCA (**Al**pharadin in **S**ymptomatic **P**rostate **C**ancer), was started in 2008 [13]. A total of 921 patients with CRPC and symptomatic bone metastases who were receiving best standard of care and were post-docetaxel or unfit for or declined docetaxel were randomized (2:1) to receive 6 injections of Radium-223 dichloride (50 kBq/kg intravenous) or matching placebo every 4 weeks. The primary endpoint was overall survival. Main secondary efficacy endpoints were time to first skeletal-related event and various biochemical end points. Based on data of an interim analysis (n=809), the study was unblinded in July 2011, since Radium-223 significantly improved OS, compared to placebo (the median OS was 14.0 vs. 11.2 months, respectively; HR=0.70; p=0.002). The updated analysis (performed in June 2012; n=921) also showed that Radium-223 significantly improved OS compared to placebo (median OS 14.9 vs. 11.3 months, respectively; HR=0.70; p<0.001). Symptomatic skeletal events (SSE) were lower in the Radium-223 arm, and time to first SSE was significantly delayed (the median time to SSE was 15.6 months, versus 9.8 months, respectively; HR= 0.66; p<0.001). A low incidence of myelosuppression was observed, with grade 3/4 events of neutropenia (3%) and thrombocytopenia (6%). Adverse events of any grade were described in 93% of the subjects who received radium-223 dichloride; versus 96% in the placebo arm (grade 3/4

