9.1.2 Secondary endpoint(s)

The secondary endpoints are:

- **Changes of pain over time** by evaluating the worst pain item as well as the subscale scores for pain severity and pain interference as determined by patient responses on the BPI-SF questionnaire. The worst pain item and subscales will be presented separately for each post-baseline assessment.
- **Changes in bone pain related quality of life** as determined by patient responses on the bone pain specific FACT-BP questionnaire. The FACT-BP score will be presented separately for each post-baseline assessment.
- **Pain control rate** as determined by the worst pain item on the BPI-SF patient questionnaire. Pain control is defined as no increase by two points from the baseline BPI-SF worst pain score.
- **Pain progression rate** as determined by the worst pain item on the BPI-SF patient questionnaire. Pain progression is defined as an increase by two points from the baseline BPI-SF worst pain score at any post baseline assessment.
- **Time to first pain progression** is defined as the time between the first injection of Radium-223 until an increase in the BPI-SF worst pain item by at least two points.
- **Time to first opioid use** in patients who did not take opioids at study entry is defined as the time from first injection of Radium-223 until first intake of opioid analgesics.
- **Evaluation of covariates on pain response** of mCRPC patients during treatment with Radium-223. The following covariates will be analyzed:
 - opioid use
 - assessment of extent of bone metastases (<6, 6-20, > 20, superscan)
 - location of bone metastases
 - level of alkaline phosphatase at baseline (<150 mU/l, 150-300 mU/l, and >300 mU/l)
 - PSA level at baseline (<50 µg/l, 50-200 µg/l, and >200 µg/l)
 - WHO pain score at baseline (WHO-Score 0+1 and WHO-Score 2+3)
 - pretreatment with chemotherapy (yes/no)
 - pretreatment with deep androgen ablation by treatment with abiraterone or enzalutamide (yes/no)
 - extent of bone uptake in known lesions (only faint, higher uptake, and strong uptake compared to surrounding bone)

- **Relation between bone uptake in known lesions and pain palliation** (only in patients with bone scan prior to start of treatment and a second scan during or within 6 weeks after end of Radium-223 treatment)
- For **Radium-223 treatment patterns** dosage and number of injections of Radium-223 will be analyzed.

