- **Course of blood counts** in patients with different extent of disease and in the whole patient population will be presented as percentage of patients below limit for further injections according to the local product information
- **Treatment-emergent Adverse Events (TEAE)** - Patients will be monitored for TEAE using the NCI-CTCAE Version 4.03. Detailed information collected for each TEAE will include: a description of the event, duration, whether the TEAE was serious, intensity, relationship to Radium-223, action taken, clinical outcome.
- **Time to next tumor treatment(s) (TTNT)** is defined as the time from the first application of Radium-223 until start of next mCRPC treatment including e.g. chemotherapy and/or hormonal treatment.
- **Time to first symptomatic skeletal event (SSE)** is defined as the time between the first injection of Radium-223 until the occurrence of first SSE defined as the first use of external beam radiation therapy to relieve skeletal symptoms, new symptomatic pathological vertebral or non-vertebral bone fractures, spinal cord compression, or tumor-related orthopedic surgical intervention
- **Overall survival** is defined as the time interval from the start of Radium-223 therapy to death, due to any cause. Patients alive at the end of the study will be censored at the last date known to be alive. Date and cause of death will be collected.

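### First SSE and time to next treatment are fixed as Kaplan-Meier summaries although death precludes both; if deaths are censored at death, the share of patients with the event is overstated

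*Protocol*

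**What the plan says.** Section 9.7.5 of the protocol chooses the estimator: "Time to event variables (TTNT, SSE, OS) will be summarized using Kaplan-Meier estimates". The output is the median and the 25th and 75th percentiles with 95% confidence intervals. A separate bullet in the same section covers pain: "Time to first pain progression will be summarized by Kaplan-Meier (KM) estimates". How censoring works is left open: "Censoring rules will be defined in the SAP".

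Section 9.1.2 defines the events, and death is not a component of any of them:

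- First SSE: "the time between the first injection of Radium-223 until the occurrence of first SSE defined as the first use of external beam radiation therapy", followed by symptomatic fractures, cord compression and tumour-related orthopaedic surgery.
- TTNT: "the time from the first application of Radium-223 until start of next mCRPC treatment including e.g. chemotherapy and/or hormonal treatment".
- First pain progression: "the time between the first injection of Radium-223 until an increase in the BPI-SF worst pain item by at least two points".

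Competing risks and cumulative incidence are not mentioned anywhere in the protocol. The background in Section 7 gives figures for the Radium-223 arm of the cited phase III trial: "median OS 14.9 vs. 11.3 months, respectively; HR=0.70; p<0.001" and "the median time to SSE was 15.6 months, versus 9.8 months, respectively". SSE, further treatment and survival are followed for up to two years after the last injection (Sections 9.1, 9.2 and 9.2.7).

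**The concern.** Kaplan-Meier treats a censored patient as someone who could still have the event later. A patient who has died cannot. When deaths are censored at death, one minus Kaplan-Meier describes a population in which nobody dies before the event. It therefore exceeds the proportion of real patients who have the event, and every percentile read from the curve comes too early.

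This matters more here than in a comparative trial. The study is single-arm and descriptive, so the curve and its percentiles are the result. Its stated aim is to describe patients in routine practice. A reader will take a two-year Kaplan-Meier figure for SSE as the share of such patients who have an SSE, and a median as the time by which half of them have had one. In a population with a median survival of little more than a year, neither reading would be right.

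**Working it through.** The protocol states no expected figure for SSE, TTNT or pain progression in this study, so there is no planned number to reproduce. The size has to come from its background medians.

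**Inputs from Section 7 (Radium-223 arm of the cited trial).** Median time to first SSE is 15.6 months. Median OS is 14.9 months.

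**Assumptions.**
- Hazards are constant.
- The 15.6 months is a median with deaths censored. The protocol does not say so.
- SSE-free patients die at a rate f times the overall death rate. f = 1 corresponds to death being independent of SSE. Smaller f allows for lower mortality before an SSE than after one.

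**Hazards.**
- SSE: h1 = ln 2 / 15.6 = 0.0444 per month.
- Death: h2 = ln 2 / 14.9 = 0.0465 per month, used as f × h2.

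**Formulas.**
- One minus Kaplan-Meier: 1 − exp(−h1 t).
- Cumulative incidence: h1/(h1 + f h2) × [1 − exp(−(h1 + f h2) t)].
- Median from the cumulative incidence: −ln(1 − 0.5/m)/(h1 + f h2), with m = h1/(h1 + f h2). It exists only if m is above 0.5.

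**SSE at 24 months, f = 1.** Kaplan-Meier: 1 − exp(−0.0444 × 24) = 0.656. Cumulative incidence: 0.0444/0.0910 × [1 − exp(−0.0910 × 24)] = 0.433. Another 0.454 would have died without an SSE.

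| f | 12 months: KM / cumulative incidence | 24 months: KM / cumulative incidence | Gap at 24 months | Median: KM / cumulative incidence |
|---|---|---|---|---|
| 1 | 41.3% / 32.5% | 65.6% / 43.3% | 22 points | 15.6 / not reached (m = 0.489) |
| 0.75 | 41.3% / 34.4% | 65.6% / 47.7% | 18 points | 15.6 / 28.1 months |
| 0.5 | 41.3% / 36.5% | 65.6% / 52.7% | 13 points | 15.6 / 21.2 months |
| 0.25 | 41.3% / 38.8% | 65.6% / 58.6% | 7 points | 15.6 / 17.8 months |

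The 25th percentile moves little: 6.5 months by Kaplan-Meier against 6.8 to 7.9 months. The distortion grows with time, and the planned follow-up reaches the times where it is large.

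**TTNT.** The protocol gives no rate. For assumed Kaplan-Meier medians of 6 to 15 months, the same formulas give a 24-month gap of 22 to 25 points with f = 1 and 7 to 8 points with f = 0.25. These figures only illustrate the range.

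**First pain progression.** The BPI-SF is completed before each injection and at one possible visit about a month after treatment (Section 9.3.1). With six four-weekly injections (assumed), that is a window of about six months. Death from any cause by then is at most about 1 − exp(−0.0465 × 6) = 24%. For an assumed Kaplan-Meier probability of 20% to 50% at six months, the gap is 2.5 to 5.7 points with f = 1 and 0.7 to 1.5 points with f = 0.25.

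**The case against.** The strongest reply is that the bias depends on a rule the protocol leaves to the SAP, which is not at hand. This stands in part. Suppose patients who die are kept at risk to their administrative end of follow-up, two years after the last injection. With administrative censoring only, one minus Kaplan-Meier then does estimate the cumulative incidence. A reader might infer that any censoring of deaths within Kaplan-Meier has the same flaw, or that overstatement is certain. The documents do not support either: the claim is conditional on censoring at death. The deferral still does not settle the matter. The estimator is already fixed, censoring at death is its usual companion, and nothing in the protocol points to another rule. Counting death as an event would depart from the definitions in Section 9.1.2.

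A reader might also infer that death is about as frequent as the event for SSE, TTNT and pain progression alike. Only SSE has a figure, and it comes from another trial's overall death rate, which includes deaths after an SSE. The 22 points are therefore the top of the range.

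It is also fair to say that Section 9.7.5 lists percentiles, not shares at fixed times. But the percentiles are affected too: the SSE median comes early by at least about two months in these scenarios.

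Finally, Section 9.9 foresees comparison with historical clinical data, for which published Kaplan-Meier medians are convenient. That is a good reason to keep those medians as a secondary display. It does not make them the right description of this cohort.

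**Conclusion.** The point holds for first SSE and TTNT, on the condition that deaths are censored at death. For SSE, the protocol's own background medians imply an overstatement of about 7 to 22 percentage points at 24 months, and 2.5 to 9 points at 12 months. The true median lies at 17.8 months or later, or is never reached, against 15.6 months by Kaplan-Meier. This rests on constant hazards, on reading 15.6 months as a death-censored median, and on a death rate in SSE-free patients between a quarter and all of the overall rate. For TTNT the direction is the same, but the protocol gives nothing from which to size it.

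Kaplan-Meier is correct for OS. For first pain progression the bias is small because the questionnaire window is short. First opioid use might seem to belong here as well, but Sections 9.7.4 and 9.7.5 state no Kaplan-Meier analysis for it, so there is no stated error to correct.

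The endpoints are secondary and descriptive. No test, error rate, sample size or primary result is affected.

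**What to change.** In Section 9.7.5:

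- Keep Kaplan-Meier for OS.
- For first SSE and TTNT, name death without the event as a competing event. Report Aalen-Johansen cumulative incidence with 95% confidence intervals at set times, for example 6, 12, 18 and 24 months.
- Keep the Kaplan-Meier medians for SSE and TTNT as a secondary display for historical comparison, with a note on how deaths were censored.
- The same approach may be used for first pain progression, but only within the BPI-SF window of about six months.

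The cost is a change of wording and standard software. Survival status and date of death are already collected (Sections 9.2.7 and 9.3.2), so no new data are needed. The downside is that the main display becomes less directly comparable with published Kaplan-Meier medians.
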